7. I am confident that I can follow through on medical treatments I may need to do at home	Disagree Strongly	Disagree	Agree	Agree Strongly	N/A
8. I understand my health problems and what causes them	Disagree Strongly	Disagree	Agree	Agree Strongly	N/A
9. I know what treatments are available for my health problems	Disagree Strongly	Disagree	Agree	Agree Strongly	N/A
10. I have been able to maintain (keep up with) lifestyle changes, like eating right or exercising	Disagree Strongly	Disagree	Agree	Agree Strongly	N/A
11. I know how to prevent problems with my health	Disagree Strongly	Disagree	Agree	Agree Strongly	N/A
12. I am confident I can figure out solutions when new problems arise with my health	Disagree Strongly	Disagree	Agree	Agree Strongly	N/A
13. I am confident that I can maintain lifestyle changes, like eating right and exercising, even during times of stress	Disagree Strongly	Disagree	Agree	Agree Strongly	N/A

Insignia Health. "Patient Activation Measure; Copyright © 2003-2010, University of Oregon. All Rights reserved."
Contact Insignia Health at www.insigniahealth.com

[figure not shown]
© Insignia Health, LLC Proprietary and Confidential © 2013 For use with a valid copyright license only
3

Visual Analogue Pain Scale (Administered Electronically via iPad or on paper)

On a scale of 0 to 10 how much pain do you currently have in your Left Hip?

(Put your pen on the red square and slide it to your pain level.)

Pain Level: 0

0  10

DONE

Back to last question

The Pain Catastrophizing Pain Scale (PCS – administered on paper)Copyright © 1995
Michael JL Sullivan**PCS**

Client No.: _____ Age: _____ Sex: M() F() Date: _____

Everyone experiences painful situations at some point in their lives. Such experiences may include headaches, tooth pain, joint or muscle pain. People are often exposed to situations that may cause pain such as illness, injury, dental procedures or surgery.

We are interested in the types of thoughts and feelings that you have when you are in pain. Listed below are thirteen statements describing different thoughts and feelings that may be associated with pain. Using the following scale, please indicate the degree to which you have these thoughts and feelings when you are experiencing pain.

0 – not at all 1 – to a slight degree 2 – to a moderate degree 3 – to a great degree 4 – all the time

When I'm in pain ...

- 1 I worry all the time about whether the pain will end.
- 2 I feel I can't go on.
- 3 It's terrible and I think it's never going to get any better.
- 4 It's awful and I feel that it overwhelms me.
- 5 I feel I can't stand it anymore.
- 6 I become afraid that the pain will get worse.
- 7 I keep thinking of other painful events.
- 8 I anxiously want the pain to go away.
- 9 I can't seem to keep it out of my mind.
- 10 I keep thinking about how much it hurts.
- 11 I keep thinking about how badly I want the pain to stop.
- 12 There's nothing I can do to reduce the intensity of the pain.
- 13 I wonder whether something serious may happen.

... Total

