- Option for patients with surgery dates less than 4 weeks prior to surgery to be enrolled in the functional testing arm only
- Option for patients who are taking Coumadin/Warfarin to be enrolled in the non-biopsy arm of the study
- Biopsies will be closed with suture and/or steri-strips
- Addition of the pain and catastrophizing questionnaire (covariate measure)

The procedure schedule can be referenced in Figure 2 (page 23, following a description of all study-related procedures and measures for Aim #2).

[figure not shown]
Primary Physiological Outcome Measures. Consistent with the Secondary Outcome Measures described in Aim #1 (please refer to Aim #1) aside from the omitted and new/ altered procedures noted above (see Changes to Study-Related Activities in this section), but followed over a longer period time (6 months).

Secondary Physiological Outcome Measures. Consistent with the *Primary Outcome Measures* described in Aim #1 (please refer to Aim #1) aside from the omitted and new/ altered procedures noted above (see Changes to Study-Related Activities in this section).

Covariate Measures. Consistent with the *Covariate Measures* described in Aim #1 (please refer to Aim #1 above), with the addition of the pain and catastrophizing scale (questionnaire)

Aim #2 Study Activities Timeline. Participants will be enrolled for up to six months prior to surgery through 6 months post-operatively. Figure 2 (next page) describes the schedule of study-related events, including evaluable time windows, under Study Aim #2.

Overview of Aim #2 study timeline, activities, measures and procedures.

Schedule of Events									
Time	-6 mo max	-8 wks to -1 wks (+ 1 day)	-1 wk (± 0 day)	TKA (Day 0)	2 wk (± 1 week)	6 wk (± 1 week)	3 mo (± 2 weeks)	6 mo (± 2 weeks)	
Enrollment	X	X							
Screening	X	X							
Questionnaires		X				X	X	X	
Functional Mobility Test		X			X	X	X	X	
Accelerometer		X ^A				X	X ^A	X ^A	
Supplement [*]			start → Stop						
Bilateral Muscle Biopsy ^B		X ^B			X			X	

Functional testing & biopsy: Performed at the [name] Lab, University of Oregon or the Slocum Center.

^A Subjects will have the accelerometer ON daily during waking hours (off while sleeping and showers) for a 7 consecutive day period ending at this time point.

^B Optional muscle biopsy as per patient choice; Biopsies must be completed a minimum of 4 weeks prior to TKA; patients who are enrolled between

-4 weeks and -1 week (+ 1 day) will not be eligible to participate in the biopsy arm.

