- Patient is 40 – 80 years old
- Patient is having a primary, unilateral TKA
- Patient has signed the current, IRB approved informed consent document
- Patient can schedule pre-operative biopsy at least 4 weeks prior to date of TKA

Exclusion Criteria – Biopsy Participant.

- In the judgment of the physicians the patient is not anticipated to have other lower extremity total joint arthroplasty before end of treatment is completed (6 months).
- Patient has had previous lower extremity total joint arthroplasty surgery within 6 months of starting -8 week to -1 week (+1 day) study activities.
- Patient has dementia or related mental issues that may potentially put the subject at risk as determined by the surgeon.
- Patient has untreated endocrine disease (hypo/hyper thyroidism, Addison's Disease or Cushing's syndrome, etc.)

- Patient has uncontrolled diabetes; defined by lab result of hemoglobin A1c level > 8.0 mg/dL. ~~at~~ If the patient has consented to biopsies, confirmation of the first step (below) must occur before patient can have pre-operative biopsy. Two-step verification process for this will occur; (1) patient self-report, with the addition of any available medical records Slocum Orthopedics has regarding patient diabetic status, and (2) Upon completion of standard of care pre-operative blood draw, we will confirm results of HbA1c. If the patient has not consented to have biopsies, the same verification process will occur before the patient begins taking the supplement.
- Patient has significant heart, liver, kidney or respiratory disease.
- Patient has peripheral vascular disease.
- Patient has active cancer.
- Patient has taken anabolic steroids in the prior six months.
- Patient has known current alcohol or drug abuse.
- Patient discharge status is known to be to care facility.
- Patient is on oral blood thinner such as Warfarin, Coumadin, Eliquis, etc.

Inclusion Criteria – Non-Biopsy Participant

- Patient is 40 – 80 years old
- Patient is having a primary, unilateral TKA
- Patient has signed the current, IRB approved informed consent document

Exclusion Criteria – Non-Biopsy Participant

- In the judgment of the physicians the patient is not anticipated to have other lower extremity total joint arthroplasty before end of treatment is completed (6 months).
- Patient has had previous lower extremity total joint arthroplasty surgery within 6 months of starting -8 to -1 week (+ 1 day) study activities.

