17	Medication Dose (1 – x)	Numeric	Data analysis, stratification, independent covariate.	1,2
18	Medication Route (1 – x)	String	Data analysis, stratification, independent covariate.	1,2
19	Medication Frequency (1 – x)	String	Data analysis, stratification, independent covariate.	1,2
20	Medication Start Date (1 – x)	Date	Data analysis, stratification, independent covariate.	1,2
21	Medication Stop Date (1 – x)	Date	Data analysis, stratification, independent covariate.	1,2
22	Health Condition (1 – x)	String	Data analysis, stratification, independent covariate.	1,2
23	Health Condition Start Date (1 – x)	Date	Data analysis, stratification, independent covariate.	1,2
24	Health Condition Stop Date (1 – x)	Date	Data analysis, stratification, independent covariate.	1,2
25	Additional procedures (1 – x)	String	Any additional medical procedures or tests performed while patient is on the study protocol; Data analysis, stratification, independent covariate.	1,2
26	Tobacco Use	Categorical	Data analysis, stratification, independent covariate.	1,2
27	Tobacco Use Frequency	Numeric	Cigarettes/day; Data analysis, stratification, independent covariate.	1,2
28	Alcohol Use	Categorical	Data analysis, stratification, independent covariate.	1,2
29	Alcohol Use Amount	Numeric	Drinks/Day of beer, wine or liquor; Data analysis, stratification, independent covariate.	1,2
30	Exercise Frequency	Categorical	Data analysis, stratification, independent covariate.	1,2
31	Charlney Classification of Disease	Categorical	Degree of disability or disease in operative and non-operative knee; Data analysis, stratification, independent covariate.	1,2

Data Elements Table. Data specifications for hospitals and practice administrative data, hospital or practice electronic medical records, and/or client self-report.				
Data Element ID	Data Element	Type	Description and Intended Use	Specific Aim #
32	Physical Therapy Utilization	Count	Data analysis, stratification, independent covariate.	1,2
33	Readmission	Dichotomous (Yes/No)	Data analysis, stratification, independent covariate.	1,2
34	Reoperation	Dichotomous (Yes/No)	Data analysis, stratification, independent covariate.	1,2
35	Clinic Visit Utilization	Count	Data analysis, stratification, independent covariate.	1,2
36	Performing Surgeon ID	Numeric	Known confounder in TKA outcome studies; Data analysis, stratification, independent covariate.	1,2

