Appendix 3: Patient-Reported Questionnaires

Social Readjustments Rating Scale – Life Events Questionnaire (Administered on paper)

Give to patient to fill out themselves or read through with patient. To measure stress according to the Holmes and Rahe Stress Scale, the number of "Life Change Units" that apply to events in the past year of an individual's life are added and the final score will give a rough estimate of how stress affects health.

Life Event	Life Change Units
Death of a spouse	100
Divorce	73
Marital separation	65
Imprisonment	63
Death of a close family member	63
Personal injury or illness	53
Dismissal from work	47
Marital reconciliation	45
Retirement	45
Change in health of family member	44
Pregnancy	40
Gain a new family member	39
Business readjustment	39
Change in financial state	38
Death of a close friend	37
Change to different line of work	36
Change in frequency of arguments	35
Major mortgage	32
Foreclosure of mortgage or loan	30
Change in responsibilities at work	29
Child leaving home	29
Trouble with in-laws	29
Outstanding personal achievement	28
Spouse starts or stops work	26
Beginning or end of school	26
Change in living conditions	25
Revision of personal habit	24
Trouble with boss	23
Change in working hours or conditions	20
Change in residence	20
Change in schools	20
Change in recreation	20
Change in church activities	19
Change in social activities	18
Minor mortgage or loan	17
Change in sleep habits	16
Change in number of family reunions	15
Change in eating habits	15
Vacation	13
Christmas	12
Minor violation of law	11

Score above 300 = At risk of illness

Score of 150 – 299 = Risk of illness is moderate (reduced by 30% from above risk)

Score < 150: Only have slight chance of illness

Holmes TH, Rahe RH (1967). "The Social Readjustment Rating Scale". *J Psychosom Res* 11 (2): 213–8. doi:10.1016/0022-3999(67)90010-4

KOOS KNEE SURVEY (Administered on paper)

Today's date: ____ / ____ / ____ Date of birth: ____ / ____ / ____

Name: _____

INSTRUCTIONS: This survey asks for your view about your knee. This information will help us keep track of how you feel about your knee and how well you are able to perform your usual activities. Answer every question by ticking the appropriate box, only one box for each question. If you are unsure about how to answer a question, please give the best answer you can.

Symptoms

These questions should be answered thinking of your knee symptoms during the **last week**.

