				

For each of the following activities please indicate the degree of difficulty you have experienced in the **last week** due to your knee.

A3. Rising from sitting

None	Mild	Moderate	Severe	Extreme
				

A4. Standing

None	Mild	Moderate	Severe	Extreme
				

A5. Bending to floor/pick up an object

None	Mild	Moderate	Severe	Extreme
				

A6. Walking on flat surface

None	Mild	Moderate	Severe	Extreme
				

A7. Getting in/out of car

None	Mild	Moderate	Severe	Extreme
				

A8. Going shopping

None	Mild	Moderate	Severe	Extreme
				

A9. Putting on socks/stockings

None	Mild	Moderate	Severe	Extreme
				

A10. Rising from bed

None	Mild	Moderate	Severe	Extreme
				

A11. Taking off socks/stocking

None	Mild	Moderate	Severe	Extreme
				

A12. Lying in bed (turning over, maintaining knee position)

None	Mild	Moderate	Severe	Extreme
				

A13. Getting in/out of bath

None	Mild	Moderate	Severe	Extreme
				

A14. Sitting

None	Mild	Moderate	Severe	Extreme
				

A15. Getting on/off toilet

None	Mild	Moderate	Severe	Extreme
				

For each of the following activities please indicate the degree of difficulty you have experienced in the **last week** due to your knee.

A16. Heavy domestic duties (moving heavy boxes, scrubbing floors, etc.)

None	Mild	Moderate	Severe	Extreme
				

A17. Light domestic (cooking, dusting, etc.)

None	Mild	Moderate	Severe	Extreme
				

Function, sports and recreational activities

The following questions concern your physical function when being active on a higher level. The questions should be answered thinking of what degree of difficulty you have experienced during the **last week** due to your knee.

SP1. Squatting

None	Mild	Moderate	Severe	Extreme
				

SP2. Running

None	Mild	Moderate	Severe	Extreme
				

SP3. Jumping

None	Mild	Moderate	Severe	Extreme
				

SP4. Twisting/pivoting on your injured knee

None	Mild	Moderate	Severe	Extreme
				

SP5. Kneeling

None	Mild	Moderate	Severe	Extreme
				

Quality of Life

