Q1. How often are you aware of your knee problem?

Never	Monthly	Weekly	Daily	Constantly
				

Q2. Have you modified your life style to avoid potentially damaging activities to your knee?

Not at all	Mildly	Moderately	Severely	Totally
				

Q3. How much are you troubled with lack of confidence in your knee?

Not at all	Mildly	Moderately	Severely	Extremely
				

Q4. In general, how much difficulty do you have with your knee?

None	Mild	Moderate	Severe	Extreme
				

Thank you very much for completing all the questions in this questionnaire.

PHQ-9 Questionnaire (Administered on paper)

Patient Name _____ Date _____

1. Over the last 2 weeks, how often have you been bothered by any of the following problems? Read each item carefully, and circle your response.

	Not at all	Several days	More than half the days	Nearly every day
	0	1	2	3
a. Little interest or pleasure in doing things				
b. Feeling down, depressed, or hopeless				
c. Trouble falling asleep, staying asleep, or sleeping too much				
d. Feeling tired or having little energy				
e. Poor appetite or overeating				
f. Feeling bad about yourself, feeling that you are a failure, or feeling that you have let yourself or your family down				
g. Trouble concentrating on things such as reading the newspaper or watching television				
h. Moving or speaking so slowly that other people could have noticed. Or being so fidgety or restless that you have been moving around a lot more than usual				
i. Thinking that you would be better off dead or that you want to hurt yourself in some way				
Totals				

2. If you checked off any problem on this questionnaire so far, how difficult have these problems made it for you to do your work, take care of things at home, or get along with other people?

Not Difficult At All	Somewhat Difficult	Very Difficult	Extremely Difficult
0	1	2	3

Oxford Knee Score (Administered Electronically via iPad or on paper)

Please answer the following 12 questions. Choose only one answer per question. The value for each answer is indicated to the right of the answer. Total up all of your answers to obtain a total score out of 48 points. Please only consider how you have been getting on during the past four weeks.

1. How would you describe the pain you have usually from your knee?	Score	8. Have you been able to do your own household shopping on your own?	Score																				

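### As printed, the KOOS and Oxford forms do not say which knee to rate, so some patients could score a different knee after surgery than before it

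*Combined protocol and SAP*

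**What the plan says.** **Role of the scores.** Under Secondary Outcome Measures for Aim #1, KOOS (on paper, for research) and Oxford (on the clinic's iPads, as routine care) are both described as knee-specific. That section does not say which knee is rated. The Aim #2 section defines its primary outcomes as "Consistent with the Secondary Outcome Measures described in Aim #1", apart from a list of omitted and changed procedures. KOOS and Oxford stay in; only the 2-week questionnaires are dropped. The Aim #2 schedule gives questionnaires before surgery and at 6 weeks, 3 months and 6 months.

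**The forms (Appendix 3).** KOOS opens with "This survey asks for your view about your knee". Its header takes date, date of birth and name, but no side. One sports item carries a qualifier, "Twisting/pivoting on your injured knee", which names neither a side nor the operated knee. Oxford begins "How would you describe the pain you have usually from your knee", and every later item that names a knee does so in the same unspecific way.

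**The other knee.** Appendix 1, element 31, records "Degree of disability or disease in operative and non-operative knee" for both aims. In Aim 2 a candidate is excluded if "Patient has had previous lower extremity total joint arthroplasty surgery within 6 months of starting" the pre-operative study activities; this stands in both the biopsy and the non-biopsy lists. Aim 1 excludes any previous replacement of the contralateral knee.

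**Analysis.** The Data Analysis section plans ANCOVA with the pretest score as covariate, and random coefficients models over the repeated visits.

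**The concern.** Every patient has one knee replaced between the baseline and the follow-up questionnaires. Before surgery that knee is usually the worse one. Afterwards a diseased knee on the other side can become the more troublesome, and an unspecific question lets the patient's attention move to it. For an Aim 2 patient with an older contralateral replacement the mechanism differs: that knee is not untreated, but after surgery there are two replaced knees to which the question could refer.

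ANCOVA on the pretest and the trajectory models both presuppose that one knee is scored throughout. If some patients switch, or blend both knees, the follow-up difference between the arms shrinks and the baseline score predicts the follow-up score less well. Neither form records which knee was rated, so the error could not be identified or corrected later. Aim 2 is the more exposed: it admits older contralateral replacements, promotes these scores to primary outcomes, and drops MRI and strength testing.

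**Working it through.** **1. Text check.** The KOOS and Oxford items, both form headers, the outcome descriptions, the eligibility lists and Appendix 1 were read for any statement of which knee to rate. None was found beyond the single sports item quoted above.

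**2. The plan's own figure.** No effect size or pre-post correlation is stated for KOOS or Oxford. The nearest figure is the Aim 2 minimally detectable effect: d = 0.79 with 40 completers per group, 85% power and two-sided 5%, falling to 0.68 at r = 0.50 and 0.52 at r = 0.75.

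- Recomputed: (1.960 + 1.036) × √(2/40) = 0.670, or 0.678 with the noncentral t. The stated 0.79 does not reproduce; it fits about 30 per group (0.787).
- The covariate step does reproduce from 0.79: 0.79 × √(1 − 0.50²) = 0.684 and 0.79 × √(1 − 0.75²) = 0.523.
- The mismatch is conservative (40 per group gives about 94% power at d = 0.79) and is separate from this point.

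**3. Dilution.** Let a fraction f in each arm rate the other knee at follow-up, and let that knee's score show a share λ (0 to 1) of the operative treatment effect Δ. The observed difference is

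(1 − f)Δ + fλΔ = Δ[1 − f(1 − λ)].

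With the variance unchanged, the sample needed for the same power is multiplied by 1/[1 − f(1 − λ)]².

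**4. Inputs.** The documents give no f; 5%, 10% and 20% are assumed. They give no λ for a knee score either. The Effect sizes paragraph gives leg-level values, non-operative over operative:

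- quadriceps volume: 1.05/1.52 = 0.69
- isometric strength: 0.66/0.90 = 0.73

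This suggests λ of about 0.7, if a knee score behaves as the leg measures do. λ = 0 is the extreme.

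| f | λ = 0.7 | λ = 0 |
|---|---|---|
| 5% | 1/0.985² = 1.03 | 1/0.95² = 1.11 |
| 10% | 1/0.97² = 1.06 | 1/0.90² = 1.23 |
| 20% | 1/0.94² = 1.13 | 1/0.80² = 1.56 |

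**5. Adding the loss of correlation, at the extreme.** Take the effect that 40 per group detects with 85% power: 0.678 × √(1 − r²), which is 0.588 at r = 0.50 and 0.449 at r = 0.75. Assume that switchers have λ = 0 and no correlation with their own baseline, so that d becomes d(1 − f) and r becomes r(1 − f). Power at f = 5%, 10% and 20% is then 80.0%, 74.4% and 62.0% for r = 0.50, and 76.5%, 67.6% and 50.9% for r = 0.75. This is an illustration of the severe end, not a forecast.

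**The case against.** The strongest reply is that the context already identifies the knee. Every patient is having a single primary replacement and fills in the forms around that operation, so many will rate the surgical knee unprompted. Nothing in the documents shows that any patient would switch. This stands, and it is why f is left as an assumption.

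The Oxford half is less certain than the KOOS half. Oxford is the clinic's routine instrument on iPads, and Appendix 3 prints a text form rather than its screens. The VAS screen in the same appendix does name a joint and a side, although the example is a left hip. The clinic's system may therefore carry laterality. The documents do not show that it does for Oxford, and the form may also be given on paper.

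Appendix 1 lists element 31 for analysis, stratification or use as a covariate, so disease in the other knee can be adjusted for. That helps with prognosis but does not reveal which knee was rated. Appendix 1 also describes KOOS and Oxford in those same terms and keeps the study endpoint label for the functional tests; their primary status in Aim 2 rests on the outcome section.

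Some stronger inferences are tempting but unsupported:

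- **That the plan expects a previous replacement of the other knee.** Aim 1 excludes it, and Aim 2 merely allows an older one.
- **That 11% to 56% is the likely cost.** That range assumes no effect on the other side, against the plan's own non-operative effects.
- **That the stated power or sample size fails.** Neither rests on KOOS or Oxford.
- **That the result would lean towards EAA.** Patients are randomised and blinded, so with no treatment effect switching should be equally common in both arms.

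**Conclusion.** The gap is real and cheap to close. As printed, KOOS and Oxford leave the rated knee to the patient, in a population where the other knee may be diseased or, in Aim 2, already replaced. The consequence is possible dilution and a weaker baseline covariate in two of several Aim 2 outcomes. It is not bias towards EAA, and no stated sample-size figure changes.

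The size depends on an unknown f. For f between 5% and 20% the sample needed for the same power rises by about 3% to 13% at λ = 0.7, and by at most 11% to 56% at λ = 0, before any loss of pre-post correlation. These figures assume the same f in both arms and an unchanged variance. The λ of 0.7 is borrowed from leg volume and strength, not from any knee score. For Oxford the finding covers the printed form only.

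**What to change.** At every visit the coordinator pre-marks *Study knee: Left / Right* on the KOOS paper form and on any paper Oxford form. Add one line asking the patient to answer about the knee that is being, or was, replaced in this study. Leave item wording and scoring unchanged. Confirm that the clinic's iPad Oxford form shows the same side, and give the same instruction there if it does not. If procedures already ensure this, write them into the protocol.

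The cost is a minor form revision with an IRB submission, and some coordination with the clinic because Oxford is its routine-care form. No visit, item or analysis is added. The Aim 2 recruitment text says that the first part of the study was completed in 2016, so the change can help Aim 2 only.
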